5.9. Sample Size and Power. The power calculations are based on our previous study and other published studies. We found an AHI reduction from 32.2 ± 5.6 SD to 24.6 ± 4.4 (7.6 or 24%) following a 12-week exercise protocol, and the attrition rate was 11%.¹⁹ The standard deviation of the change in AHI was large (13), perhaps because of the relatively short intervention duration and small sample size compared with what are proposed. In a recent meta analysis of the effect of dietary weight loss on AHI, we find an average reduction of AHI of 34% in studies involving weight loss of approximately 10% over intervention durations of 12-20 weeks.¹⁸ Based on this finding, we assume a reduction of total AHI from 32.2 ± 5.6 to 21.25 ± 5.2 following the Weight Loss Alone treatment (10.9 or ~34% reduction). A previous study indicated a 46% reduction in total AHI (from 21.7 ± 9.0 to 11.8 ± 6.8) following exercise and weight loss.²⁷ Based on these data, in calculating power, we assume decreases in AHI of increasing magnitude will be observed following exercise alone, weight loss alone, and exercise + weight loss. We assume a reduction of AHI from 32.2 ± 5.6 to 17.3 ± 5.2 (14.9 or 46% reduction) after exercise + weight loss, and we assume 10% attrition. In our power calculations, the overall significance level is set at $\alpha = 0.05$. To insure we will have sufficient testing power, order-restricted tests are not considered in power estimation, but this type of testing will be applied in our data analyses to test the hypothesized pattern.

To ensure power for the **Primary Hypothesis (Compared with exercise alone and weight loss alone, exercise+weight loss will elicit significantly greater improvements in AHI)** we consider weight loss alone vs. exercise+weight loss. We set the significance level at 0.025 to adjust for multiple testing. With $n=30$

per treatment, the power is 86% to detect an average difference of 4 (14.9 vs 10.9, or 46% vs 34%) in AHI reduction between the treatments assuming treatment standard deviations of 5. The power is 82.2% with a 10% attrition. We expect higher statistical power to compare exercise alone vs. exercise+weight loss.

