5.10. Statistical Analysis. We will first examine univariate and bivariate statistics to determine the distributional characteristics of study variables and to identify potentially relevant background covariates and confounders. For the **Primary Hypothesis and Secondary Hypotheses 1 and 3**, we will use an analysis of covariance (ANCOVA) approach to examine treatment effects on post-intervention (i.e., immediate post-test for Primary Hypothesis and Secondary Hypothesis 3; 3-month follow-up for Secondary Hypothesis 1) outcome values (i.e., AHI scores for Primary Hypothesis and Secondary Hypothesis 1; comorbidity measures for Secondary Hypothesis 3), with treatment as the primary independent variable, and adjusting for baseline outcome value, intervention dose (percentage of sessions attended), baseline outcome value, age, sex,

duration of OSA diagnosis, plus any other relevant covariates. We will test for ordering of treatment means (not adjusted for covariates) via order-restricted tests within the R package flexisoreg. Next, we will test for overall differences among treatment groups on post-treatment AHI values with order-restricted comparisons (isotonic contrasts) of covariate-adjusted means to test for the predicted ordered patterning of the three treatment means. For **Secondary Hypothesis 2**, we will examine the effect of time point (pre- vs. post-treatment) on AHI scores at each treatment level (i.e., test “simple main effects” of time) in the context of a repeated measures ANCOVA. Analyses will be based on an intent-to-treat plan. For each hypothesis, overall alpha will be set at .05, with a Bonferroni correction applied when multiple non-independent tests are conducted. **Missing data** due to dropout or other causes will be addressed with analyses of multiply-imputed datasets generated with SAS PROC MI based on models drawing on all available participant data.

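### The predicted ordering of the three arms is tested twice, unadjusted and adjusted, with no deciding test named; this costs power in the better test or, if Bonferroni is not applied, raises the error rate modestly

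*Combined protocol and SAP*

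**What the plan says.** Section 5.10 names ANCOVA as the approach for the Primary Hypothesis and for Secondary Hypotheses 1 and 3, and then sets out two ordering tests in sequence.

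- First: "We will test for ordering of treatment means (not adjusted for covariates", using order-restricted tests in a named R package. This sentence does not name the outcome.
- Next: a test of "overall differences among treatment groups on post-treatment AHI values" by "order-restricted comparisons (isotonic contrasts) of covariate-adjusted means to test for the predicted ordered patterning of the three treatment means".

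The adjusted model contains the baseline value, age, sex and duration of diagnosis. It also contains the share of sessions attended, which is measured after randomisation, and an open-ended clause for further covariates.

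The same section gives a general multiplicity rule: "For each hypothesis, overall alpha will be set at .05, with a Bonferroni correction applied when multiple non-independent tests are conducted". It does not list which tests form a family.

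Section 5.9 leaves order-restricted tests out of the power calculation but says that "this type of testing will be applied in our data analyses to test the hypothesized pattern". The level set there ("We set the significance level at 0.025 to adjust for multiple testing") belongs to the pairwise comparisons of the Primary Hypothesis.

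**The concern.** Both steps are described as tests of the same predicted pattern. Neither is called confirmatory, supportive or descriptive, neither gates the other, and nothing says what follows if they disagree. Two readings are open.

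- The Bonferroni rule covers the pair. The error rate is then safe, but half the alpha goes to an unadjusted version of the same question, and the adjusted test is held to 0.025.
- The rule is not applied to the pair, and a significant result on either test is taken as support. The ordering claim then has two chances to succeed, and its error rate exceeds 5%.

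At stake is the credibility of any claim that the benefit increases from exercise to weight loss to the combination.

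**Working it through.** **1. The plan's own figure.** No power is stated for the ordering tests. The nearest figure is the pairwise power in section 5.9 (difference 4, SD 5). The noncentrality is 4/(5·√(2/30)) = 3.10 with 30 per arm and 4/(5·√(2/27)) = 2.94 with 27 per arm. A t-test at one-sided 0.025 gives 86.1% and 82.2%, matching the stated 86% and 82.2%.

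**2. Inputs for the ordering tests.** The number per arm is 27 (30 less 10% attrition). The assumed AHI reductions are 7.6, 10.9 and 14.9 (section 5.9). The baseline-to-post correlation is not stated, so two scenarios were derived.

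- *Plan's SDs:* baseline 5.6, post 5.2, change 5. r = (5.6² + 5.2² − 5²)/(2 × 5.6 × 5.2) = 33.40/58.24 = 0.573. The unadjusted variance is 1/(1 − 0.573²) = 1.49 times the adjusted variance.
- *Spread of the earlier trial:* section 5.9 gives a change SD of 13, but SDs of 5.6 and 4.4 cannot produce a change SD above 5.6 + 4.4 = 10, so those ± values cannot be ordinary SDs. Section 4.1.2.3 gives g = −0.45 for a net difference of 7.6 + 4.5 = 12.1, where 4.5 = 28.9 − 24.4 in the control arm. If g is that difference over a raw SD, the SD is 12.1/0.45 = 26.9. Then r = 1 − 13²/(2 × 26.9²) = 0.883, and the residual SD is 26.9 × √(1 − 0.883²) = 12.6.

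**3. The test.** The three means are fitted under the predicted order. The statistic is T = n·Σ(fitted mean − grand mean)²/s². It is computed on raw post-treatment AHI, on change from baseline, and on post-treatment AHI adjusted for baseline AHI. Critical values come from simulation under no difference. The adjusted version uses baseline AHI only, without the plan's other covariates. The pair is treated as its own family.

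**4. Error rate of the pair under no difference.**

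| Scenario | Either counts at 0.05, unadjusted test on post values | Either counts at 0.05, unadjusted test on change | Both at 0.025, post values |
|---|---|---|---|
| Plan's SDs (r 0.573) | about 7.5% | about 7% | 3.8% |
| Earlier trial's spread (r 0.883) | 8.9% | 6.0% | 4.6% |

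With post values and r from 0.3 to 0.9, the either-counts error runs from 6.3% to 9.0%, and the Bonferroni error from 3.2% to 4.6%. A single ordering test has 5%.

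**5. Power.**

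| Scenario | Unadjusted (post values), 0.05 | Adjusted, 0.05 | Adjusted, 0.025 | Unadjusted (post values) and adjusted disagree at 0.05 |
|---|---|---|---|---|
| Plan's SDs, full effects | about 100% | about 100% | about 100% | under 0.1% |
| Plan's SDs, half the effects | 79% | 91% | 84% | about 15% |
| Earlier trial's spread, full effects | 24% | about 64% | about 52% | about 47% |

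In the last row, if the unadjusted test uses change scores, its power is about 63% and disagreement falls to about 8%.

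**The case against.** Four points can be made for the plan.

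- **The Bonferroni sentence already covers this.** Two tests of one ordering on the same patients fit its wording, and error then stays below 5%. This stands. A reader might infer that the plan as written inflates the error rate. The text does not support that: inflation arises only if the rule is not applied to the pair. An unadjusted test alone does not inflate error in a randomised trial.
- **The large power contrast depends on assumptions.** A reader might infer that the unadjusted test is badly underpowered, at 24% against about 64%. That needs an SD of about 27, back-calculated from a g that section 4.1.2.3 does not define. It also needs the unadjusted test to use post-treatment values. The preceding ANCOVA sentence favours that reading, but section 5.9 frames effects as reductions. On change scores the contrast is 63% against 64%, and on the plan's own SDs and full effects there is no loss. This stands.
- **The unadjusted test is not redundant.** A reader might infer that it adds nothing. It is the only planned ordering test free of session attendance and of covariates chosen later. This stands, and it shapes the fix.
- **The ordering test is not the primary comparison.** The Primary Hypothesis sets the combination against each single treatment and is powered pairwise. This also stands.

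Reporting unadjusted and adjusted results side by side is common practice, but the plan calls both of them tests and does not label either as supportive.

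**Conclusion.** The concern holds as a gap in the analysis plan with a modest, conditional cost. The ordering is tested twice and no deciding test is named.

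- **With Bonferroni on the pair:** error is about 3.8% to 4.6%. The price is power in the adjusted test: none at the plan's full effects and SDs, 91% to 84% at half those effects, and about 64% to 52% with the earlier trial's spread.
- **Without it, either test counting:** error is about 7.5% to 9% if the unadjusted test uses post-treatment values, or 6% to 7% if it uses change scores.

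These figures assume 27 per arm, an isotonic test of the form above, correlations derived rather than stated, and adjustment for baseline AHI only. They therefore describe the adjusted test as it should be, not the plan's model with session attendance in it. The pairwise primary comparisons are not affected.

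**What to change.** In section 5.10, name one confirmatory ordering test: order-restricted, on post-treatment AHI, adjusted for baseline PSG AHI and the pre-randomisation stratification factors in section 5.5 (age group, sex, screening AHI group). Exclude session attendance and the open-ended covariate clause from that model; making the existing adjusted test primary as it stands would not be a clean remedy.

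Report the unadjusted means descriptively, or as a supportive analysis that spends no alpha, and state whether they are post-treatment values or changes.

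The cost is SAP wording only: no extra data or patients, and one fewer confirmatory test.

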For **Secondary Hypothesis 1, Compared with exercise alone and weight loss alone, exercise + weight loss will elicit significantly greater improvements in OSA at 3-month follow-up**, we anticipate decreases in compliance, resulting in greater within-treatment variability and/or lower between-treatment differences, and less powerful between-treatment tests. As such, we consider 82% to be an upper bound power estimate of this hypothesis. If, for example, at follow-up, the magnitude of the effect of condition were only 80% of that anticipated at post-test, power to detect significant differences would be approximately 65%.

For **Secondary Hypothesis 2, Compared with baseline, each treatment will elicit significant improvements in AHI**, the power calculation is based on paired one-sided t-tests to test the reduction of AHI. Since there are 3 treatments, multiple-testing Bonferroni-adjusted significance level is set at $0.05/3=0.017$. For exercise alone, from our preliminary data, we set the mean±SD reduction in AHI (baseline minus post-treatment) at 7.6 ± 12.5 (24% reduction) for the power calculation. The standard deviation is smaller than in our preliminary study because of the longer duration and larger sample size. With $n=30$, tests should have power of 86.0% to detect such a post-exercise difference. With 10% attrition, our tests should have power of 82% to detect this change. Also, we propose a 16 wk treatment, which is a longer than in our previous study and may result in larger reduction with smaller variance. We expect that the AHI reduction will be at least as great as seen in our previous study. Because we expect that weight loss alone and exercise+weight loss will elicit larger effects than exercise alone, the power to detect changes in AHI will be greater for these other treatments.

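### Section 5.10 names no test of exercise + weight loss against each single treatment, and the ordered tests it does name cannot by themselves settle the primary hypothesis

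*Combined protocol and SAP*

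**What the plan says.** Section 5.9 states the primary hypothesis as a two-part superiority claim: "Compared with exercise alone and weight loss alone, exercise+weight loss will elicit significantly greater improvements in AHI". For power, "we consider weight loss alone vs. exercise+weight loss", and "We set the significance level at 0.025 to adjust for multiple testing". The stated power is 86% with 30 per arm and 82.2% after 10% attrition, for a difference of 4 with SD 5. The other comparison is mentioned without a figure: "We expect higher statistical power to compare exercise alone vs. exercise+weight loss".

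The same section gives ordered tests a separate role: "order-restricted tests are not considered in power estimation", but "this type of testing will be applied in our data analyses to test the hypothesized pattern".

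Section 5.10 covers the primary hypothesis and Secondary Hypotheses 1 and 3 with an ANCOVA in which treatment is the main factor. It then describes order-restricted tests of the unadjusted means, followed by a test of overall group differences in post-treatment AHI using "order-restricted comparisons (isotonic contrasts) of covariate-adjusted means to test for the predicted ordered patterning of the three treatment means". It names neither E+WL versus WL nor E+WL versus exercise, does not repeat 0.025 and gives no sidedness. A general clause sets overall alpha at .05 per hypothesis and applies Bonferroni where several non-independent tests are run, but it does not list those tests.

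**The concern.** A claim that the combination beats each component needs evidence on two specific differences. A global test of three means, ordered or not, addresses a different question: whether the means differ at all, or differ in the predicted direction. It can reject because of any one gap. The plan's own assumptions build in such a gap, since it expects reductions of 7.6 with exercise and 10.9 with WL.

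An analyst who follows 5.10 as written could therefore obtain a significant ordered result and report it as support for the primary hypothesis when the combination adds nothing to weight loss. That would be the trial's headline claim. Secondary Hypothesis 1 (follow-up AHI) has the same form and the same analysis.

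**Working it through.** **Inputs from 5.9.** Mean AHI reductions: exercise 7.6, WL 10.9, E+WL 14.9. SD 5 for the primary power calculation. SDs of change for exercise: 13 (previous study) and 12.5 (Secondary Hypothesis 2). There are 30 per arm, or 27 after 10% attrition.

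**Step 1: reproduce the stated power.** Two-sample t-test, noncentrality = difference / (SD × √(2/n)), 2n − 2 df.
- n = 30: 4 / (5 × √(2/30)) = 4 / 1.291 = 3.10. One-sided 0.025 gives 86.1%; two-sided 0.025 gives 78.5%.
- n = 27: 4 / (5 × √(2/27)) = 4 / 1.361 = 2.94. One-sided 0.025 gives 82.2%; two-sided 0.025 gives 73.5%.

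The stated 86% and 82.2% are thus pairwise figures at one-sided 0.025, which is numerically the same as two-sided 0.05. For Secondary Hypothesis 1, the plan says that at 80% of the effect "power to detect significant differences would be approximately 65" per cent. A difference of 0.8 × 4 = 3.2 at one-sided 0.025 gives 68.4% (n = 30) and 63.6% (n = 27), which bracket that figure. This too is consistent with a pairwise comparison.

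**Step 2: let the combination add nothing to WL.** Set the reductions to 7.6, 10.9 and 10.9, with n = 27 and alpha 0.05. Use a change-score model without covariates and pooled variance on 78 df.
- Isotonic test: fit the means under exercise ≤ WL ≤ E+WL by pooling adjacent violators. The statistic is the between-arm sum of squares of the fitted means divided by the total sum of squares. The simulated 5% critical value is 0.0476, with 500,000 replicates per scenario.
- Three-arm F test: the grand mean is 29.4/3 = 9.8, so the deviations are −2.2, 1.1 and 1.1. Noncentrality = 27 × (4.84 + 1.21 + 1.21) / SD² = 196.0 / SD², which is 7.84 at SD 5, 1.25 at SD 12.5 and 1.16 at SD 13.
- Direct contrast: E+WL minus WL at one-sided 0.025.

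| Rejection rate | SD 12.5 | SD 13 | SD 5 |
|---|---|---|---|
| Isotonic test | 25% | 24% | 82% |
| Three-arm F test | 15% | 14% | 69% |
| Direct E+WL vs WL | 2.5% | 2.5% | 2.5% |

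With all three means equal, the isotonic test rejects at its nominal 5%. If E+WL is 1 unit worse than WL (7.6, 10.9, 9.9), it still rejects in 66% of trials at SD 5.

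**Step 3: Secondary Hypothesis 1.** Scaling by 0.8 gives 6.08, 8.72 and 8.72. The isotonic test rejects in 18-19% of trials at SD 12.5-13 and in 65% at SD 5. The direct contrast stays at 2.5%. (This 65% is a rejection rate with no added benefit. It is unrelated to the plan's 65% power.)

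**Step 4: what the direct contrasts deliver under the plan's 7.6, 10.9 and 14.9 (n = 27).**

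| Proportion significant | SD 5 | SD 12.5-13 |
|---|---|---|
| Both contrasts, one-sided 0.025 | 83% | 16-18% |
| Both contrasts, two-sided 0.025 | 74% | 10-11% |
| Isotonic test, 0.05 | nearly 100% | 62-65% |

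**The case against.** The strongest reply is that this is one combined document and 5.9 already settles the matter. It names both pairwise comparisons, sets 0.025 and confines ordered testing to the hypothesized pattern. The Bonferroni clause in 5.10 is compatible with two contrasts at 0.05/2, and the ANCOVA has a treatment factor from which they could be drawn. This stands as far as intent goes. A reader might infer that the pairwise tests were abandoned in favour of ordered ones, but the documents do not support that. The fault is that the analysis section never names the deciding tests.

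Second, the term isotonic contrasts is undefined. If it meant separate step contrasts, one step would be WL versus E+WL. However, 5.10 speaks of overall differences and the patterning of three means, which reads as a global test. The simulated rates belong to one such test and would differ for another.

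Third, a reader might infer that the ordered test has an inflated type I error. It does not: when exercise and WL differ, rejecting equality is correct. The error lies in concluding that the combination beats WL.

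Fourth, covariate adjustment will change the rates. By how much cannot be derived from 5.9. Its ± figures for exercise, 5.6 and 4.4, taken as SDs, allow a change SD of at most 5.6 + 4.4 = 10.0, yet it reports 13. No residual SD can safely be built from such inputs.

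**Conclusion.** The point holds as a gap between 5.9 and 5.10 that should be fixed. The omission of the deciding contrasts is plain from the text. Its consequence depends on assumptions: a likelihood-ratio isotonic test, no covariates, a common SD, 27 per arm, and the plan's exercise-WL gap of 3.3. On those, a trial in which the combination adds nothing would give a significant ordered result in 24-25% of cases at SD 12.5-13 and in 82% at SD 5, against 2.5% for the direct contrast.

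Sidedness is a related open item. Section 5.9 states one-sided tests only for Secondary Hypothesis 2. The primary power figures match one-sided 0.025, but they equally match a two-sided 0.05 calculation to which no split was applied. A reader might conclude that the stated power is wrong. The documents show only that it depends on an unstated choice.

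**What to change.** In 5.10:

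1. Name the covariate-adjusted contrasts E+WL minus WL and E+WL minus exercise as the tests that decide the primary hypothesis and Secondary Hypothesis 1. Report both with confidence intervals.
2. Label the order-restricted tests, unadjusted and adjusted, as supportive tests of the predicted pattern, and define the isotonic contrasts.
3. State the level and sidedness of each contrast and restate power to match. One-sided 0.025 keeps 86%/82.2%. Two-sided 0.025 gives 78.5%/73.5%.
4. State the decision rule. The 0.025 in 5.9, described as a multiplicity adjustment, fits two separate claims with a Bonferroni split. If both contrasts must be significant, no split is needed and the 5.9 wording should be changed to say so.

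The change is to wording, with no new data collection. Sample size is unaffected if one-sided 0.025 is what was meant. If two-sided 0.025 was meant, the sponsor must accept the lower power or revisit the sample size. The real cost is that the ordered test's higher rejection rate no longer supports the primary claim. At SD 12.5-13, the chance of winning both contrasts is 10-18%, depending on sidedness, against 62-65% for the ordered test.
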